13.2.8.2. Analyses of Secondary Efficacy Endpoints

Summary statistics for each secondary efficacy endpoint will be provided by cohort using the FAS. Analyses of the secondary efficacy endpoints are presented as follows:

- The complete TMA response will be summarized with the number and percent of responders during the treatment period (induction and maintenance) and an exact binomial two-sided 95% confidence interval for the complete TMA response rate by cohort.
- The duration of complete TMA response will be based on the subjects who achieve a complete TMA response. If the last laboratory measurement is the last consecutive measurement of the complete TMA response, the duration will be censored at the date of the last laboratory measurement. The Kaplan-Meier method will be used to estimate the distribution. Median duration will be estimated with two-sided 95% confidence interval using the complementary log-log transformation [Collett 1994].
- The time to complete TMA response will be analyzed by the Kaplan-Meier method. Subjects who do not achieve a complete TMA response during study will have their event time censored at the last laboratory measurement. Median time to the complete TMA response will be estimated with two-sided 95% confidence interval using the complementary log-log transformation [Collett 1994]. The complete TMA response rates at 26 weeks, 1 year and 2 years will be estimated with two-sided 95% confidence interval using the Kaplan-Meier method.
- The number and percent of subjects achieving TMA event-free status will be summarized with two-sided exact binomial 95% confidence interval. Subjects whose TMA event-free status cannot be evaluated (e.g., early dropouts or death) will be considered as not achieving TMA event-free status.
- The time to TMA event-free status will be analyzed by the Kaplan-Meier method. Subjects who do not achieve a TMA event-free status during study will have their event time censored at the last visit. Median time to the TMA event-free status will be estimated with two-sided 95% confidence interval using the complementary log-log transformation [Collett 1994]. The TMA event-free status rates at 26 weeks, 1 year and 2 years will be estimated with two-sided 95% confidence interval using the Kaplan-Meier method.

CONFIDENTIAL

No use, disclosure or reproduction outside of Omeros without prior written authorization

- The number and percent of subjects who achieve an increase in eGFR from baseline of $> 15 \text{ ml/min}/1.73 \text{ m}^2$ will be summarized with two-sided exact binomial 95% confidence interval. Subjects whose eGFR cannot be evaluated (e.g., early dropouts or death) will be considered as not achieving the required increase in eGFR.
- The time to increase in eGFR from baseline of $> 15 \text{ ml/min}/1.73 \text{ m}^2$ will be analyzed by the Kaplan-Meier method. Subjects who do not achieve an increase in eGFR from baseline of $> 15 \text{ ml/min}/1.73 \text{ m}^2$ during study will have their event time censored at the last laboratory measurement. Median time to the increase in eGFR from baseline of $> 15 \text{ ml/min}/1.73 \text{ m}^2$ will be estimated with two-sided 95% confidence interval using the complementary log-log transformation [Collett 1994]. The increase in eGFR from baseline of $> 15 \text{ ml/min}/1.73 \text{ m}^2$ rates at 26 weeks, 1 year and 2 years will be estimated with two-sided 95% confidence interval using the Kaplan-Meier method.
- The number and percent of subjects achieving hematological normalization will be summarized with two-sided exact binomial 95% confidence interval. Subjects whose hematological normalization status cannot be evaluated (e.g., early dropouts or death) will be considered as not achieving hematological normalization.
- The time to hematological normalization will be analyzed by the Kaplan-Meier method. Subjects who do not achieve hematological normalization during study will have their event time censored at the last laboratory measurement. Median time to hematological normalization will be estimated with two-sided 95% confidence interval using the complementary log-log transformation [Collett 1994]. The hematological normalization rates at 26 weeks, 1 year and 2 years will be estimated with two-sided 95% confidence interval using the Kaplan-Meier method.
- The number and percent of subjects achieving TMA remission will be summarized with two-sided exact binomial 95% confidence interval. Subjects whose TMA remission status cannot be evaluated (e.g., early dropouts or death) will be considered as not achieving TMA remission.
- The 5 dimensions of EQ-5D-5L will be summarized with frequency and percentage by visit and cohort. The EQ-5D-5L Visual Analogue scale (EQ VAS) and its change from baseline will be summarized with descriptive statistics by visit and cohort. The t-distribution will be used to calculate the two-sided 95% confidence interval for the mean change from baseline.
- Change from baseline of key laboratory parameters (LDH and haptoglobin) will be summarized with descriptive statistics and two-sided 95% confidence interval for the mean change using t-distribution.
- The rate of TMA interventions will be summarized with descriptive statistics and two-sided 95% confidence interval for the mean rate using t-distribution.

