7.3.2. Secondary Endpoints

- Safety as assessed by AEs, SAEs, vital signs, ECGs, physical examinations, and laboratory measures
- Complete TMA response defined as normalization of platelet count, normalization of serum LDH, and > 25% decrease in serum creatinine on at least 2 consecutive measures over at least 4-weeks
- Duration of complete TMA response measured from the time of the first measurement of complete TMA response to the last consecutive measurement of complete TMA response
- Time to complete TMA response measured by the time to reach the first measurement of complete TMA response
- TMA event-free status during treatment defined as no decrease in platelet count of > 25% from baseline, no plasma exchange or plasma infusion, and no initiation of new dialysis for at least 12 consecutive weeks
- Time to TMA event-free status measured by the time to reach the first documented TMA event-free status from the first dose of OMS721
- Increase of > 15 ml/min/1.73 m² in eGFR calculated by the MDRD Equation for subjects aged ≥ 18 years and the Schwartz equation for subjects < 18 years
- Time to eGFR increase of > 15 ml/min/1.73 m² measured by the time to reach the first measurement increase in eGFR of > 15 ml/min/1.73 m² from the first dose of OMS721
- Hematological normalization defined as normalization of platelet count and normalization of serum LDH on at least 2 consecutive measurements over at least 4 weeks
- Time to hematological normalization measured by the time to reach the first measurement of hematological normalization from the first dose of OMS721
- TMA remission defined as platelet count ≥ 150,000/µL on at least 2 consecutive measures over at least 2 weeks
- Quality of life as measured by EQ-5D-5L

CONFIDENTIAL

No use, disclosure or reproduction outside of Omeros without prior written authorization

- Serum creatinine change from baseline
- Serum LDH change from baseline
- Serum haptoglobin change from baseline
- Rate of TMA interventions defined as the number of dialysis events, plasma infusion events and plasma exchange events per subject per day over the treatment period
- PK of OMS721
- PD of OMS721
- ADA

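### Should the Kaplan-Meier response rates in protocol section 13.2.8.2 treat death before response as a competing event?

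*Protocol*

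**What the plan says.** Protocol section 13.2.8.2 gives four response endpoints a time-to-event analysis: complete TMA response, TMA event-free status, an eGFR increase above 15 ml/min/1.73 m², and hematological normalization. Each has a Kaplan-Meier median and Kaplan-Meier rates at three landmarks, as in "The complete TMA response rates at 26 weeks, 1 year and 2 years will be estimated with two-sided 95% confidence interval".

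The censoring rules are:

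- complete TMA response: "Subjects who do not achieve a complete TMA response during study will have their event time censored at the last laboratory measurement";
- event-free status: "Subjects who do not achieve a TMA event-free status during study will have their event time censored at the last visit";
- hematological normalization: "Subjects who do not achieve hematological normalization during study will have their event time censored at the last laboratory measurement";
- eGFR increase: the same rule, at the last laboratory measurement.

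The same section also plans a number and percent with an exact binomial interval for each endpoint. For three of them it says how death is counted: "Subjects whose TMA event-free status cannot be evaluated (e.g., early dropouts or death) will be considered as not achieving TMA event-free status"; "Subjects whose eGFR cannot be evaluated (e.g., early dropouts or death) will be considered as not achieving the required increase in eGFR"; and "Subjects whose hematological normalization status cannot be evaluated (e.g., early dropouts or death) will be considered as not achieving hematological normalization". The complete TMA response bullet has no such sentence.

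Protocol section 13.2.1 describes all data summaries as descriptive. The abbreviated SAP, written after the study was discontinued, states in section 9.1 that efficacy will not be analyzed. The secondary parameters kept in its section 4.2 are safety and the changes in creatinine, LDH and haptoglobin.

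**The concern.** Kaplan-Meier assumes that a censored subject has the same future chance of responding as those still at risk. A subject who has died has none. With such deaths censored, one minus the Kaplan-Meier estimate is never below the cumulative incidence of response, and it lies above it as soon as a response follows a death.

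Two features make this look like more than a technicality. For three endpoints, the curve censors a death that the paired binary analysis counts as a failure, so one section can give two response rates that treat the same subject in opposite ways. And event-free status requires "no plasma exchange or plasma infusion, and no initiation of new dialysis for at least 12 consecutive weeks", so if it is documented only once those weeks are complete, every death before Week 12 comes before it could be achieved.

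At stake would be landmark rates that are too high and median times that are too short, in a single-arm study of a disease which protocol section 5.1.2 says can be fatal if untreated.

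**Working it through.** The documents give no planned rate, median or death rate for these endpoints, so there is no figure to reproduce. Every death and response rate below is an assumption.

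**Inputs.** n = 56 (the planned resistant cohort, protocol section 13.1). Visit days come from protocol section 10.1.4, with Day 183 taken as Week 26. Assumed: response share R = 50%; response times uniform over Weeks 1-24 (Days 7-168) and recorded at the next visit; death share D = 2, 5 or 10%; no other losses.

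**Hand check.** If 28 of 56 respond and d deaths all precede the first response, the Kaplan-Meier rate is 28/(56 − d). For d = 1 this is 28/55 = 50.9%, and for d = 3 it is 28/53 = 52.8%, against 28/56 = 50.0%.

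**Closed form, deaths unrelated to response.** Let f be the chance that a would-be responder who dies does so before the response visit. In expectation Kaplan-Meier returns R and the cumulative incidence is R − f × R × D, so the excess is f × R × D.

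- Deaths uniform over Weeks 1-20 (Days 7-140): f is the mean of (visit day − 7)/133, capped at 1, which is 0.645.
- Deaths uniform over 104 weeks (728 days): the mean response visit is Day 98.8, so f = 98.8/728 = 0.136.

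| Deaths | Excess, Weeks 1-20 | Excess, 104 weeks |
|---|---|---|
| 2% | 0.645 × 50 × 0.02 = 0.65 points | 0.136 × 50 × 0.02 = 0.14 points |
| 5% | 0.645 × 50 × 0.05 = 1.61 points | 0.136 × 50 × 0.05 = 0.34 points |
| 10% | 0.645 × 50 × 0.10 = 3.23 points | 0.136 × 50 × 0.10 = 0.68 points |

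Simulation with 4000 runs per case gave 0.6, 1.6 and 3.2 points for Weeks 1-20, in agreement.

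**Other cases, by simulation, at 2, 5 and 10% deaths.**

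- Only never-responders die, in Weeks 1-20: 0.8, 2.0 and 4.3 points at Week 26. Over 104 weeks: roughly 0.2, 0.4 and 0.8.
- Event-free status documented over Weeks 12-24, deaths in Weeks 1-20: 0.9, 2.3 and 4.5 points.
- Responses over Weeks 1-100 and deaths over 104 weeks: 0.5, 1.3 and 2.5 points at 2 years.
- All deaths after Week 26: no excess at Week 26.
- Median, with 60% responding: the Kaplan-Meier median is earlier in 0.8, 5.2 and 16.6% of runs, and reached only by Kaplan-Meier in 0.1, 2.3 and 6.8%. It is otherwise unchanged.

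**Heavy mortality.** With constant hazards over 2 years, set L = −ln(1 − R − D); the Kaplan-Meier rate is then 1 − exp(−L × R/(R + D)). For R = 0.5 and D = 0.2, L = −ln 0.3 = 1.204 and the rate is 1 − exp(−0.860) = 57.7%, an excess of 7.7 points.

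**Scale.** The exact 95% interval for 28 of 56 is 36% to 64%, about 14 points either side.

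**Does any planned output use these estimates?** Under the protocol, only secondary descriptive tables would. Under the SAP, none does: section 9.1 excludes efficacy, and section 4.2 names none of the four endpoints.

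**The case for a change.** The best case for a change is that the direction of the error is certain, the protocol counts deaths in two ways within one section, and the remedy is cheap. Aalen-Johansen cumulative incidence needs only reworded bullets, and deaths are already recorded under protocol section 12.3.2. Abandoning an analysis does not make its specification right, and the text could be reused. Nor is the effect bound to be small: at 20% deaths it is 7.7 points.

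The mechanism and the mismatch with the binary rules stand. Three things weaken the case for acting.

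- The larger Week 26 figures put every death in Weeks 1-20, on top of the response window. Exclusion 14, which bars subjects expected to live under 3 months, points away from that. Spreading deaths over the treatment period cuts the excess to about a fifth. The full analysis set also requires a post-baseline platelet count, first scheduled on Day 4, so some of the earliest deaths enter neither estimate.
- A competing-event rule for death alone would not reconcile curve and proportion. The binary rules also count early dropouts as failures, while the curves would still censor them, including subjects withdrawn to receive eculizumab. With 50% responding and deaths plus withdrawals at 30%, the constant-hazard formula gives 1 − exp(−1.609 × 0.5/0.8) = 63.4%, so that gap can be the larger one.
- The share who respond over the treatment period was to be reported directly, with exact intervals, beside every curve.

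**Conclusion.** The observation is technically correct, but a change brings no gain. If these analyses were run and any death preceded a later response, the Kaplan-Meier rates would be too high and the medians could be too early. With 2 to 10% deaths, the Week 26 excess is 0.14 to 0.68 points if deaths are spread over 104 weeks and 0.6 to 3.2 points if they all fall in Weeks 1-20. For event-free status it could reach 4.5 points. These sizes rest on assumed death and response rates; only the direction is firm.

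The conclusion rests on the abbreviated SAP governing what is analyzed. It runs none of the four analyses, so rewording the protocol bullets would alter no table, estimate or conclusion. Should the protocol text be reused or these curves be produced after all, cumulative incidence with death before response as a competing event would be the better estimator, and dropouts would still be handled differently from the binary analyses.

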13.2.9. Pharmacokinetic Analyses

Standard pharmacokinetic analyses will be performed and will be described in a Pharmacokinetic Analysis Plan.

CONFIDENTIAL

No use, disclosure or reproduction outside of Omeros without prior written authorization

13.2.10. Pharmacodynamic Analyses

The extent of *ex vivo* lectin pathway activation will be calculated relative to the subject's baseline (pre-dose) result. The lectin pathway activity of post-dose samples is expressed as % inhibition relative to baseline. The lectin pathway activity will be summarized.

13.2.11. Pharmacokinetic-Pharmacodynamic Analyses

The relationship between OMS721 concentration and lectin pathway activity will be plotted.

13.2.12. Immunogenicity Analyses

The presence of ADA and neutralizing antibodies will be summarized by cohort.

13.2.13. Safety Analyses

13.2.13.1. Extent of Exposure

The following exposure items will be summarized with descriptive statistics by route (IV and SC) and cohort using the safety analysis set:

- Cumulative doses in milligrams taken by treatment period (the Treatment Induction Period, the Treatment Maintenance Period and the entire treatment period).
- Duration of treatment in weeks by treatment period, which is defined as (the last dose date of the treatment period – the first dose date of the treatment period + 1)/7.
- The number of vials used.
- The intended number of vials.
- Absolute dose intensity (ADI), which is defined as the actual dose taken in milligrams per week by treatment period. (ADI = Cumulative doses taken in milligrams /Duration of treatment in weeks).
- Intended dose intensity (IDI), which is defined as the initial assigned dose in milligrams per week by treatment period. The IDI of the IV route during the Treatment Induction Period is $2 \times 370 = 740$ mg/week if supplemental IV doses are not given. The IDI of the SC route during the Treatment Induction Period and the Treatment Maintenance Period is $150 \times 7 = 1050$ mg/week.
- Relative dose intensity (RDI), which is defined as the ADI as a percentage of the IDI by treatment period. (RDI = ADI/IDI $\times 100$).

13.2.13.2. Adverse Events

The incidence of all reported AEs and treatment-related AEs will be tabulated by cohort. AEs will be classified by system organ class and preferred term using the Medical Dictionary for Regulatory Activities (MedDRA). For incidence reporting, if a subject reported more than one AE that was coded to the same system organ class or preferred term, the subject will be counted only once for that specific system organ class or preferred term. A treatment-emergent AE (TEAE) is defined as an event that first occurs or worsens in intensity after the administration of study drug.

CONFIDENTIAL

No use, disclosure or reproduction outside of Omeros without prior written authorization

An overview of AEs, which includes subject incidence of TEAEs, treatment-related AEs, AEs related to study procedures, SAEs, death, and AEs leading to discontinuation, will be presented by cohort.

The subject incidence of treatment-related AEs will be summarized by system organ class and preferred term.

AEs judged to be related to protocol procedures or study conduct by the Investigator will be listed.

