5.3. Potential Risk and Benefits

5.3.1. Known and Potential Risks

5.3.1.1. Human MASP-2 Deficiency

MASP-2 deficiency has been reported to occur in humans and the clinical phenotype of MASP-2 deficiency may be relevant to risk assessment of MASP-2 inhibition with OMS721. The literature contains conflicting reports as to whether subjects with MASP-2 deficiency are at risk for adverse effects.

Two case reports described individuals with MASP-2 deficiency due to a homozygous mutation (D120G) with clinical associations with autoimmunity or recurrent bacterial infections; one patient was healthy until 13 years of age and the other patient had cystic fibrosis [Olesen 2006, Stengaard-Pedersen 2003]. A genetic screen of 335 Polish children with recurrent respiratory tract infections identified one child with MASP-2 deficiency [Cedzynski 2004]. In contrast, in a genetic screen of 868 healthy Spaniards, two homozygous D120G individuals were identified; both subjects were healthy without clinical evidence of recurrent infections or autoimmune disorders and both had normal levels of circulating complement [Garcia-Laorden 2006].

CONFIDENTIAL

No use, disclosure or reproduction outside of Omeros without prior written authorization

The gene frequency of the D120G mutation is 2-4% in European populations, which would predict that approximately one in 625 to 2000 individuals in this population would be homozygotes with MASP-2 deficiency [Garcia-Laorden 2006, Thiel 2007]. Polymorphisms in the MASP-2 gene as well as the plasma concentration of MASP-2 are influenced by race. For example, the D120G mutation is the most common one in Caucasians but it is not found in Chinese or Africans [Thiel 2007]. Moreover, the circulating levels of MASP-2 were lowest in Africans (median 196 ng/mL), followed by Chinese (262 ng/mL), and Amerindian (290 ng/mL), and highest in Caucasian Danes (416 ng/mL) [Thiel 2007]. The initial studies were in Danes and a plasma concentration below 100 ng/mL was suggested as indicating MASP-2 deficiency since only individuals homozygous for the D120G mutation had this level. Subsequent studies in broader populations showed that this cutoff was inappropriate since 5% of Chinese and 19% of Africans tested had values below 100 ng/mL.

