10.2.1.5. Suspected Infection

Since increased susceptibility to infections is a potential risk of inhibiting MASP-2 activity, subjects should be closely monitored for symptoms or signs of infection. If the subject is suspected to have developed an infection, empiric antimicrobial therapy should be promptly initiated along with appropriate microbiological testing to identify the source of infection.

CONFIDENTIAL

No use, disclosure or reproduction outside of Omeros without prior written authorization

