13.2.13.3. Serious Adverse Events

Serious adverse events will be listed and summarized in the same manner as all AEs. Events with a fatal outcome will be listed.

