10. SAFETY AND TOLERABILITY

10.1. Overall Summary of Safety

An overall summary of treatment-emergent adverse events, which is defined as the AEs occurring or worsening after the start of study treatment, will be provided by cohort. All AEs will be coded by MedDRA. The following items will be included in the overall summary:

- Subject incidence of treatment-emergent AEs
- Subject incidence of treatment-related AEs (defined as probable or possible related to study drug)
- Subject incidence of treatment-emergent AEs by maximum CTCAE grade
- Subject incidence of treatment-emergent serious AEs (SAEs)
- Subject incidence of treatment-emergent AEs leading to discontinuation of study drug
- Subject incidence of treatment-emergent AEs leading to discontinuation of study
- Subject incidence of treatment-emergent fatal AEs
- Total number of unique treatment-emergent AE MedDRA preferred terms
- Median number of unique treatment-emergent AE MedDRA preferred terms per subject
- Total number of unique treatment-emergent SAE MedDRA preferred terms
- Median number of unique treatment-emergent SAE MedDRA preferred terms per subject

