10.2. Adverse Event Preferred Term and Body/Organ System Summary Tables

Subject incidence of the following treatment-emergent AEs will be provided by cohort:

- Pre-treatment AEs will be summarized by MedDRA SOC and preferred term (pre-treatment AEs are those AEs that occurred prior to the start of study treatment)
- treatment-emergent AEs by MedDRA SOC, and preferred term
- treatment-emergent AEs by MedDRA preferred term
- treatment-related AEs by MedDRA SOC, and preferred term
- treatment-emergent AEs by MedDRA preferred term, and maximum CTCAE grade
- AEs leading to study drug discontinuation by MedDRA SOC, and preferred term
- AEs leading to study discontinuation by MedDRA SOC, and preferred term
- treatment-emergent SAEs by MedDRA SOC, and preferred term
- treatment-related SAEs by MedDRA SOC, and preferred term

Omeros Corporation

Statistical Analysis Plan (Abbreviated) - Protocol No. OMS721-HUS-002

- AEs leading to death by MedDRA SOC, and preferred term

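### Adverse event tables count subjects or unique terms, so repeat non-serious infections under one preferred term appear in no specified output

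*Protocol*

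**What the plan says.** Protocol 13.2.13.2 states the counting rule for incidence reporting: "if a subject reported more than one AE that was coded to the same system organ class or preferred term", then "the subject will be counted only once for that specific system organ class or preferred term". Protocol 13.2.13.3 carries this over to serious events and adds a listing: "Serious adverse events will be listed and summarized in the same manner as all AEs". Fatal events are also listed there, and 13.2.13.2 lists events related to study procedures or conduct.

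The abbreviated SAP opens its section 10.2 tables with "Subject incidence of the following treatment-emergent AEs will be provided by cohort". The only rows in SAP 10.1 that count anything other than subjects use unique terms: "Total number of unique treatment-emergent AE MedDRA preferred terms" and "Median number of unique treatment-emergent AE MedDRA preferred terms per subject", with matching rows for serious events.

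On the risk itself, Protocol 10.2.1.5 says "Since increased susceptibility to infections is a potential risk of inhibiting MASP-2 activity" and asks for close monitoring. Protocol 5.3.1.1 reports two case reports of MASP-2 deficiency with "clinical associations with autoimmunity or recurrent bacterial infections", and describes the literature as conflicting. Protocol 12.3.1 requires onset date, duration and severity for each adverse event.

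**The concern.** If a drug raises susceptibility to infection, one way this can show is as more episodes in the same subjects. A subject with one upper respiratory infection and a subject with five, all coded to the same term, add the same single count to every planned table. The tables by maximum CTCAE grade also keep one grade per subject. Efficacy analysis has been dropped (SAP 4.1 and 9.1), and safety is the first item among the parameters that SAP 4.2 keeps. The safety tables are therefore most of what the study will report, and on this named risk they drop information that the case report forms hold.

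**Working it through.** **Step 1. Does any planned output show a repeat episode?** The plan states no figure to reproduce, so the check is a reading of each output.

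| Output | Second non-serious episode, same preferred term | Second episode, different preferred term |
|---|---|---|
| Incidence by SOC (Protocol 13.2.13.2, SAP 10.2) | no change | no change in the SOC row |
| Incidence by preferred term | no change | adds to another row |
| Maximum CTCAE grade (SAP 10.1, 10.2) | changes only if the grade is higher | adds to another row by term |
| Unique-term counts (SAP 10.1) | no change | can add to the per-subject count |
| Listing of serious events (Protocol 13.2.13.3) | not included | not included |

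A serious repeat would be in that listing. Neither document specifies a listing of all adverse events, an episode count, or an event rate. Treatment duration is summarised (Protocol 13.2.13.1, SAP 10.3) but is not joined to adverse events.

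**Step 2. What the rule hides, by direct count.** Assume that 20 of the 80 planned subjects have infections under one term. The table reads 20/80 = 25% whether each has 1, 2, 3 or 5 episodes. The episodes number 20, 40, 60 or 100.

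**Step 3. How much is lost, by assumed rate.** The documents give no infection rate, so a range is shown. With Poisson episodes at rate r per year over T years, the expected subject incidence is 1 − exp(−rT). For T = 2 (the planned 104 weeks):

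| Rate doubled | Incidence before | Incidence after | Ratio |
|---|---|---|---|
| 0.1 to 0.2 per year | 1 − exp(−0.2) = 18.1% | 1 − exp(−0.4) = 33.0% | 1.82 |
| 1 to 2 per year | 1 − exp(−2) = 86.5% | 1 − exp(−4) = 98.2% | 1.14 |
| 2 to 4 per year | 98.2% | 1 − exp(−8) = 99.97% | 1.02 |

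Expected episodes double in every row. If subjects differ in their underlying rate (negative binomial with k = 1), incidence is 1 − 1/(1 + rT). That gives 66.7%, 80.0% and 88.9% at 1, 2 and 4 per year, with ratios 1.20 and 1.11.

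For T = 0.5 (26 weeks), doubling from 1 to 2 per year moves incidence from 1 − exp(−0.5) = 39.3% to 1 − exp(−1) = 63.2%, a ratio of 1.61. Shorter follow-up therefore weakens the loss.

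**Step 4. Subjects with repeats.** Take 80 subjects over 110 weeks (104 plus the 6 weeks to the second follow-up visit), so T = 110/52.18 = 2.108 years, with all infections under one term. With m = rT, expected episodes are 80m, subjects counted are 80[1 − exp(−m)], and subjects with two or more episodes are 80[1 − exp(−m)(1 + m)].

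| Rate per year | Episodes | Subjects counted | Subjects with 2 or more |
|---|---|---|---|
| 0.1 | 16.9 | 15.2 | 1.5 |
| 0.5 | 84.3 | 52.1 | 22.7 |
| 1 | 168.6 | 70.3 | 49.8 |

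At 0.1 per year little is lost. At 0.5 per year about 23 subjects with repeat infections would look like single cases.

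**The case against.** Counting a subject once per term is the ordinary meaning of subject incidence, and the protocol limits the rule to incidence reporting. This stands: the rule is not an error, and the only weakness is that no event-level line accompanies it.

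A reader might infer that the protocol expects harm in the form of recurrent infection. It does not say so. The association comes from two case reports; one patient was healthy until age 13 and the other had cystic fibrosis. A Spanish study cited in 5.3.1.1 found similar allele frequencies in healthy subjects and in children with recurrent respiratory infections. The section concludes that the literature gives no clear indication of risk. Section 10.2.1.5 names susceptibility to infection and does not mention recurrence. Nor can infection be ranked as the main potential harm, because the clinical data section (5.3.1.3) is not readable in the public text.

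A reader might also infer that all recurrence vanishes. Step 1 shows otherwise: repeats under different terms fill separate rows, and serious repeats are listed. The data monitoring committee also reviews serious events as they occur and cumulative data every four months (Protocol 10.4). These points stand and narrow the gap to non-serious repeats under one term, and to the SOC row.

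Finally, the study is uncontrolled, so no comparison of infection rates between arms is planned, and SAP 2 says that it was discontinued before a meaningful number of patients could be enrolled. The ratios above therefore only illustrate how insensitive incidence can be, and two-year saturation is largely moot. With few subjects, individual records can be read directly, but only if some output presents them, and none is specified for non-serious events.

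**Conclusion.** The point holds in a limited form. The planned summaries cannot show repeat infections under the same preferred term, and the SOC row cannot show repeats at all. Serious repeats remain visible in the listing that the protocol specifies, although SAP 10.1 and 10.2 do not restate that listing.

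The size depends on the rate, which must be assumed: negligible near 0.1 infections per subject-year and substantial at 0.5 or more, if follow-up were as long as planned. A general claim that subject incidence saturates is not supported, because it needs rates of about 1 per year or higher over the full two years. The early stop makes the practical weight low. The change is still worth making, because it is cheap and concerns a risk that the protocol names.

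**What to change.** Keep the incidence tables. In SAP 10.2 add one table for the SOC Infections and infestations, by cohort, on the safety analysis set, with:

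- the total number of treatment-emergent episodes;
- the number of subjects with 0, 1, 2, or 3 or more episodes;
- the same lines for serious infections and for infections of CTCAE grade 3 or higher.

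State that repeat episodes of one preferred term count separately, and that records of one ongoing episode are merged before counting, with the merging rule written down.

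The cost is the SAP wording, one table and the merging step. Onset, duration and severity are already recorded, so no new data or visits are needed. Under Protocol 13.2 a change of analysis method needs a protocol amendment only if it alters a principal feature, and an added descriptive table should not. The change affects reporting only and leaves treatment and monitoring as they are.
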